
Descriptive statistics (number, mean, standard deviation, coefficient of variation [%CV], minimum, median, and maximum) will be used to summarize serum rituximab concentration data by treatment and study day at

each planned sampling time point. The PK parameters calculated from the serum rituximab concentrations will also be summarized by treatment and study day using descriptive statistics.

Plots of the mean and individual serial serum rituximab concentrations over time by treatment and study day, as well as trough concentrations, will be provided following i.v. infusions.

The geometric means of the primary PK parameters ($AUC_{0-168,1}$ and $AUC_{0-168,4}$) will be compared between SAIT101 and rituximab (MabThera[®]) using analysis of variance. The statistical analysis of the loge-transformed primary endpoints will be based on an analysis of variance model. Covariates (e.g., age, sex, body weight, etc.) may be added to the planned analysis. Least-squares geometric means will be presented for each treatment with corresponding 95% CIs. The ratio of least-squares geometric means (SAIT101/rituximab) will be presented with corresponding 90% CIs. Pharmacokinetic similarity will be concluded if the ratio of least-squares geometric means fall between 80.00% and 125.00% for both primary parameters. Estimates and CI will also be provided for secondary C_{max} and C_{trough} (Day 29) parameters.

Pharmacodynamic analyses:

The PD analysis will be performed on the PK/PD sub-population.

Descriptive statistics (n, mean, standard deviation, %CV, minimum, median, maximum, and 95% confidence intervals [CIs]) will be used to summarize CD19+ B cell count, IgG and IgM data (observed change from baseline and percent change from baseline) by treatment and study day at each planned sampling time point. The PD parameters calculated from observed change from baseline and percent change from baseline will also be summarized by treatment and study day using descriptive statistics.

Plots of the mean and individual observed change from baseline and percent change from baseline CD19+ B cell count over time by treatment and study day will be provided following i.v. infusions.

The means of PD parameters will be compared between SAIT101 and MabThera[®] using analysis of covariance.

Sample size:

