Allowing for a 4% drop-out rate and patients with major protocol deviations as seen in the Ardeshta et al², 147 patients in each group will give 80% probability of demonstrating the equivalence in the PP set.

At least 154 patients per arm (308 patients overall) should be randomized into the study. With 154 patients, the estimated ORR with 95% CI of SAIT101 is 77% (70%-84%). ORR with 95% CI of rituximab based on a random effect meta-analysis that include Ardeshta et al. 2014, Kahl et al. 2014 and Colombat et al. 2001 was estimated as 72% (68%-76%). Maximum difference in upper and lower 95% CI of ORRs is $\pm 15.0\%$, which is smaller than the margin $\pm 16.0\%$, and therefore estimated ORR with 95% CI of SAIT101 is considered to be clinically relevant.

Pharmacokinetic/pharmacodynamic sub-population

Pharmacokinetic variability for both AUC and C_{max} in the LTBFL population is estimated to be approximately 18% based on a randomized, open-label, multi-center study in 24 CD20 positive diffuse large B-cell lymphoma patients.

For PK, assuming a CV of 38% in both AUC_{0-168} , based on Regazzi et al. 2005²³ and no true difference between SAIT101 and rituximab in this parameter, 60 evaluable patients per arm are required to yield 81% overall power for comparison of $AUC_{0-168, 1}$ and $AUC_{0-168, 4}$ between the test and comparator treatments, using the standard two one-sided testing procedure, a 5% significance level for each one-sided test (90% CI). To ensure 120 evaluable patients are available, a total of 134 patients will be randomized for the PK/PD sub-population.

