The geometric means of the primary PK parameters ($AUC_{0-168,1}$ and $AUC_{0-168,4}$) will be compared between SAIT101 and MabThera[®] using analysis of variance. The statistical analysis of the loge-transformed primary endpoints will be based on an analysis of variance model. Covariates (e.g., age, sex, body weight, and etc.) may be added to the planned analysis. Least-squares geometric means will be presented for each treatment with corresponding 95% CIs. The ratio of least-squares geometric means (SAIT101/MabThera[®]) will be presented with corresponding 90% CIs. Pharmacokinetic similarity will be concluded in the ratio of least-squares geometric means falls between 80.00% and 125.00% for both primary parameters. Estimates and CI will also be provided for C_{max} and C_{trough} (Day 29) parameters.

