#### **Pharmacokinetic/ Pharmacodynamic sub-population**

For PK, assuming a coefficient of variation (CV) of 38% in both  $AUC_{0-168}$ , based on Regazzi et al. 2005 and assuming no true difference between SAIT101 and MabThera® in this parameter, 60 evaluable patients per arm are required to yield 81% overall power for comparison of  $AUC_{0-168, 1}$  and  $AUC_{0-168, 4}$  between the test and comparator treatments, using the standard two one-sided testing procedures, a 5% significance level for each one-sided test (90% CI). To ensure 120 evaluable patients are available, a total of 134 patients will be randomized for the PK/PD sub-population.

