$AUC_{0-168,w1}$  and  $AUC_{0-168,w4}$  will be considered as primary PK endpoints and the other parameters will be secondary.

---

Document:

Author:

Version Number:

Version Date:

Final v1.0

10Sep2019

Template No: CS\_TP\_BS016 Revision 4

Effective Date: 01Apr2016

Reference: CS\_WI\_BS005

All primary and secondary PK parameters will be listed and summarized by treatment and study week using n, mean, SD, standard deviation, CV%, minimum, median, maximum, and geometric mean, geometric CV%, except that  $t_{max}$  will be reported with n, minimum, median, and maximum only.

The additional following summaries of PK parameters will be generated:

- By treatment and region (EU, Other including US)
- By treatment and age category (18-60 years and >60 years)
- By treatment and sex
- By treatment and overall ADA status.

The geometric means of the primary PK parameters ( $AUC_{0-168,w1}$  and  $AUC_{0-168,w4}$ ) will be compared between SAIT101 and MabThera® using analysis of variance on the loge-transformed parameters with fixed effect for treatment. No covariates will be included. Least-squares geometric means will be presented for each treatment with corresponding 95% CIs. The ratio of least-squares geometric means (SAIT101/MabThera®) will be presented with corresponding 90% CIs. Pharmacokinetic similarity will be concluded if the ratio of least-squares geometric means falls between 80.00% and 125.00% for both primary parameters. Estimates and CI will also be provided for  $C_{max,w1}$ ,  $C_{max,w4}$ , and  $C_{trough}$  (Day 29) parameters using the same methods.

A sensitivity analysis will be performed for the above PK comparisons, in which the above comparison will be replicated, with the addition of the following covariates to the statistical model: age, sex, overall ADA status, body weight at baseline.

Scatter plots of individual and geometric mean primary PK parameters  $AUC_{0-168,w1}$ ,  $AUC_{0-168,w4}$ ,  $C_{max,w1}$  and  $C_{max,w4}$  will be presented. Additional, graphical presentations of PK data may be added at the discretion of the PK scientist, if further illustration of the PK results is deemed appropriate.

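### PK similarity is decided on the point estimate of the ratio, not on its 90% confidence interval, so the 5% test behind the sample size is never applied

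*SAP*

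**What the plan says.** The decision rule for PK similarity appears in three places, always in terms of the ratio alone.

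- SAP 13.2: "Pharmacokinetic similarity will be concluded if the ratio of least-squares geometric means falls between 80.00% and 125.00% for both primary parameters".
- Protocol 8.11: "Pharmacokinetic similarity will be concluded in the ratio of least-squares geometric means falls between 80.00% and 125.00% for both primary parameters".
- Protocol synopsis, pharmacokinetic analyses: "Pharmacokinetic similarity will be concluded if the ratio of least-squares geometric means fall between 80.00% and 125.00% for both primary parameters".

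In each place the preceding sentence gives the 90% interval a reporting role only. In SAP 13.2 the ratio "will be presented with corresponding 90% CIs".

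The sample-size text has a different basis. Protocol 8.4 uses the "standard two one-sided testing procedure" at 5% per one-sided test, corresponding to a 90% interval, and obtains 81% overall power for the two AUC0-168 parameters with 60 evaluable patients per arm. The synopsis and SAP 2.3 repeat this. SAP 6.3 declines a multiplicity adjustment for PK because regulators fix the significance level and because the power calculation already covers both comparisons.

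For the primary efficacy endpoint, protocol 8.2 and SAP 16.1.3 do require the 95% interval for the ORR difference to lie within ±16%.

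**The concern.** Two one-sided tests at 5% are equivalent to requiring the whole 90% interval to lie inside the limits. A rule that looks only at the estimate ignores its uncertainty and does not hold the error rate at 5%. No sentence in either document makes the PK conclusion depend on the interval, so the plan sizes the PK comparison for one test and decides it by another.

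The two AUC0-168 parameters are the primary PK endpoints of a biosimilarity trial. Under the written rule the sponsor could declare similarity for a product whose exposure lies at or beyond the limit. If the estimate fell inside the limits while its interval crossed one of them, the two parts of the plan would give opposite answers, and someone would have to choose between them after seeing the data.

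**Working it through.** **Inputs.** CV 38%, true ratio 1.00, 60 evaluable patients per arm, 5% per one-sided test and 81% overall power (protocol 8.4, SAP 2.3). Limits 80.00–125.00% (SAP 13.2), which are ±ln(1.25) = ±0.2231 on the log scale.

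**Standard error.** Log-scale SD = √ln(1 + 0.38²) = 0.3673. SE of the log ratio = 0.3673 × √(2/60) = 0.0671.

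**Reproducing the plan's 81%.** Power of the interval rule for one parameter at a true ratio of 1.00 is 2Φ(0.2231/0.0671 − 1.645) − 1 = 0.908 by normal approximation, or 0.904 by simulation with the t distribution on 118 degrees of freedom. With the two parameters taken as independent, 0.908² = 0.824 and 0.904² ≈ 0.818. Both agree with 81% to within 2 percentage points, so the stated power belongs to the interval rule.

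**Power of the written rule.** The chance that the estimate lies inside the limits is Φ((ln 1.25 − μ)/SE) − Φ((−ln 1.25 − μ)/SE), where μ is the log of the true ratio. At μ = 0 this is 0.9991 per parameter and 0.9991² ≈ 0.998 for both if independent. That is not the planned 81%.

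**Pass probability per parameter at or beyond the lower limit:**

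| True ratio | Written rule (estimate) | Interval rule (90% CI) |
|---|---|---|
| 0.80 | 50.0% | 5.0% |
| 0.75 | 16.8% | 0.5% |
| 0.70 | 2.3% | 0.01% |

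The figures at a true ratio of 1.25 match those at 0.80. The 50% does not depend on the CV: 0.80 is the limit itself, so the estimate falls on either side equally often. It stays at 50% with the 18% variability that protocol 8.4 also mentions.

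**Both parameters at a true ratio of 0.80.** Similarity requires both AUCs to pass. The correlation between their estimates is not given, so it is varied here as an assumption.

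| Correlation | Written rule, both pass |
|---|---|
| 0 | 25% |
| 0.5 | 33% |
| 0.8 | 40% |
| 1 | 50% |

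The interval rule gives 0.05² = 0.25% if independent and at most 5%.

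**What each rule accepts.** The half-width of the 90% interval on the log scale is 1.658 × 0.0671 = 0.111. For the interval to fit, the observed ratio must lie between exp(−0.223 + 0.111) = 0.894 and exp(0.223 − 0.111) = 1.118. The written rule accepts 0.80 to 1.25. An observed ratio of 0.81 passes as written, although its 90% interval is about 0.72 to 0.91.

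**The case against.** The strongest reply is that the interval was obviously meant. The sample-size text names the procedure and the level, SAP 6.3 treats the PK comparisons as inferential at a regulatory level, the 90% interval appears in the sentence just before the decision rule, and the protocol copies contain slips of grammar that suggest hurried drafting. The interval will also be reported, so any reader could apply the proper test. PK is a secondary objective in a sub-population, and the ORR conclusion is untouched.

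Most of this is fair. A drafting error is the likeliest explanation, and the 81% power supports it. But the sentence is the operative rule. It stands in three places and was carried into a final SAP that changed other parts of the same PK analysis, fixing the primary model without covariates and adding a sensitivity analysis with them. Reporting the interval does not settle which rule decides. The contrast with the ORR rule, where the interval is placed within the margin explicitly, leaves the PK text without support on its own terms.

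It is also true that 50% is a per-parameter figure. For the overall conclusion the range is 25–50%, and 50% is its upper end.

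**Conclusion.** The concern holds. As written, PK similarity depends on the estimated ratio alone, and the 5% two one-sided tests appear only in the sample-size justification. At a true ratio of 0.80 the written rule passes each parameter 50% of the time instead of 5%, and both parameters 25–50% of the time instead of at most 5%. The joint range rests on an unstated correlation; the per-parameter figure at the limit does not depend on the CV. The other figures assume the plan's CV of 38%, 60 evaluable patients per arm and normally distributed log AUC. This must be corrected because it is the success criterion for both primary PK parameters. It does not affect the ORR analysis.

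**What to change.** Replace the decision sentence in SAP 13.2, protocol 8.11 and the synopsis with wording such as: *PK similarity is concluded only if the 90% confidence interval for the geometric mean ratio (SAIT101/MabThera) lies wholly inside 80.00–125.00% for each of the two AUC0-168 parameters.* Use each document's own labels: suffixes w1 and w4 in the SAP, 1 and 4 in the protocol.

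The cost is one sentence in three places. The two protocol copies need an amendment under protocol 10.7. If the protocol is not reopened, correct SAP 13.2 and record the change in SAP 2.6, where departures from the protocol are already listed. Either way it should be done before the PK results are unblinded. Sample size, data collection and the analysis model stay the same, and the stated 81% power then describes the test that is applied.

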## 13.2. PHARMACOKINETIC PARAMETERS

For PK parameter calculations on Week 1, predose samples that are BLQ or missing will be assigned a numerical value of zero. Any anomalous concentration values observed at predose over the 1st dosing interval will be identified in the study report and used for the computation of PK parameters. Pharmacokinetic parameters will be computed if the anomalous concentration is not greater than 5% of the observed maximum concentration ( $C_{\text{max}}$ ). If the anomalous concentration is greater than 5% of  $C_{\text{max}}$ , the PK parameters for the given patient will be calculated and reported in the listing, but excluded from statistical summaries and analyses. On week 4, predose sample that is BLQ will be assigned a numerical value of zero. Missing predose sample will be set to missing.

The following PK parameters will be calculated for rituximab for each treatment by non-compartmental methods using actual elapsed time from dosing, if possible.

$AUC_{0-168,w1}$	Area under the serum concentration-time curve (AUC) over the 1 st dosing interval on Week 1 from time zero (predose) to the time prior to the 2 nd dose (168 hours postdose) ( $\mu\text{g}\cdot\text{h}/\text{mL}$ ), calculated by linear up/log down trapezoidal summation. This parameter will only be calculated if at least the 2 postdose concentrations (the end of infusion and Week 2 predose) are available and evaluable.
$AUC_{0-168,w4}$	Area under the serum concentration-time curve (AUC) over the 4 th dosing interval on Week 4 from time zero (predose) to 168 hours postdose ( $\mu\text{g}\cdot\text{h}/\text{mL}$ ), calculated by linear up/log down trapezoidal summation. This parameter will only be calculated if all 3 concentrations (predose, the end of infusion, and Week 5) are available and evaluable.
$C_{\text{max},w1}$	Maximum serum concentration ( $\mu\text{g}/\text{mL}$ ) over the 1 st dosing interval on Week 1, obtained directly from the observed concentration versus time data. This

---

Document:

Author:

Version Number:

Final v1.0

Version Date:

10Sep2019

Template No: CS\_TP\_BS016 Revision 4

Reference: CS\_WI\_BS005

Effective Date: 01Apr2016

	parameter will only be reported if the end-of-infusion concentration is available and evaluable.

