## 15. Exploratory Analysis of ADA on PK and PD

An exploratory statistical assessment of the impact of overall ADA status (positive or negative) on PK across treatments will be completed by adding this covariate to the model used in the primary statistical analysis.

Overall ADA status will be defined as ADA positive if a positive ADA result occurred at any timepoint up to Week 28 (for Week 28 analysis for PK and PD and for final analysis for PK only) or up to Week 52 (for PD, final analysis). Subjects without a positive ADA result at any timepoint are considered ADA negative.

The ratio of geometric means for ADA positive/ADA negative will be reported with the 90%

---

Document:

Author:

Version Number:

Version Date:

Final v1.0

10Sep2019

Template No: CS\_TP\_BS016 Revision 4

Effective Date: 01Apr2016

Reference: CS\_WI\_BS005

CI for this ratio. Descriptive statistics for rituximab concentrations and the primary PK parameters will also be presented by ADA status. Mean PK profiles will be plotted by treatment and ADA status on linear and semi-log concentration scales.

The impact of ADA on PD (observed CD19+ B cell counts) will be explored graphically. Mean PD profiles will be plotted by treatment and overall ADA status on a linear scale.

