### 18.1. ADA

The incidence of ADA and neutralizing antibody at Day 1 pre-dose and at Weeks 2 pre-dose, 3 pre-dose, 4 pre-dose, Week 5, 12, 20, 28, 36, and 52 (EOS) will be summarized by treatment group and visit.

- Incidence (%)= number of subjects with specific assessment result/ number of subject with available assessment results \* 100%

ADA and neutralizing antibody results by visit as well as the overall positive of ADA and neutralizing antibody from Day 1 will be summarized. Patients with at least one positive result up to Week 28 (or Week 52) from (and including) Day 1 will be considered as overall positive; Otherwise, patients without any positive result up to Week 24 (or Week 52) from (and including) Day 1 will be considered as overall negative.

For each treatment group, the proportion of response, 95% CI for the proportion, proportion difference between SAIT101 and MabThera®, standard deviation, and 95% CI for the proportion difference will be reported. The Wilson Score method will be used to calculate 95% CI.

- Response:
  - ADA positive
  - ADA negative
  - Neutralizing antibody positive
  - Neutralizing antibody negative

Listings for ADA assessments by patient will be provided.

---

Document:

Author:

Version Number:

Version Date:

Final v1.0

10Sep2019

Template No: CS\_TP\_BS016 Revision 4

Effective Date: 01Apr2016

Reference: CS\_WI\_BS005

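### The PK sensitivity analysis adjusts the treatment ratio for ADA status counted up to Week 28, although the AUCs end by Day 29; the primary PK conclusion is not affected

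*SAP*

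**What the plan says.** SAP 13.2 bases PK similarity on an analysis of variance of the log-transformed AUCs with treatment as the only term: "No covariates will be included". It then adds: "A sensitivity analysis will be performed for the above PK comparisons, in which the above comparison will be replicated". The added terms are "age, sex, overall ADA status, body weight at baseline". The purpose of this model is therefore to re-estimate the SAIT101/MabThera ratio.

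SAP 13.2 does not define overall ADA status, but SAP 15 does: "Overall ADA status will be defined as ADA positive if a positive ADA result occurred at any timepoint up to Week 28". For PK this window applies at both the Week 28 and the final analysis, and a patient with no positive result is classed as negative. SAP 18.1 makes the start of the window explicit by counting positives "from (and including) Day 1 will be considered as overall positive"; the Day 1 sample is taken before dosing.

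The first AUC runs up to the second dose. The fourth runs to the Week 5 sample: "This parameter will only be calculated if all 3 concentrations (predose, the end of infusion, and Week 5) are available and evaluable".

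Immunogenicity is a secondary objective (Protocol 2.2, SAP 2.1.2), and SAP 18.1 reports the between-arm difference in ADA proportions with a 95% CI. ADA status at baseline is listed separately among the baseline characteristics in SAP 9. Protocol 8.11 offers age, sex and body weight as example PK covariates, in an open-ended list that does not name ADA.

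**The concern.** Age, sex and baseline weight are fixed before dosing, so adjusting for them leaves the randomised comparison intact. ADA status up to Week 28 is different. It can be affected by the product, and part of it can arise after the exposure being modelled has ended. A first positive at Week 20 cannot have altered the Week 1 AUC, yet it would enter the model for that AUC.

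Two errors are possible. If one product provokes more early antibodies and these lower exposure, conditioning on ADA removes a real product difference. If low exposure leads to later ADA and the arms differ in ADA rate, conditioning creates a difference that does not exist. In both cases the check is least reliable when immunogenicity differs between the products, which is when a biosimilar trial most needs it. What is at stake is the only analysis that SAP 13.2 labels a sensitivity analysis of the treatment ratio.

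**Working it through.** **Plan's own figure.** Inputs from SAP 2.3: CV 38%, 60 evaluable patients per arm, true ratio 1.00, one-sided 5% for each test. The 80–125% limits are from SAP 13.2.
- Log-scale SD = sqrt(ln(1 + 0.38²)) = 0.367.
- Exact power of the two one-sided tests with 118 df: 90.4% for one AUC.
- Both AUCs, treated as independent: 0.9039² = 81.7%, against 81% stated. The figure is reproduced, and it does not depend on the sensitivity covariates.

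**Timing** (visit days from Protocol Table 1, ADA sampling from SAP 18.1).
- Week 28 is Day 190. That is 190 − 8 = 182 days (26 weeks) after the first AUC ends and 190 − 29 = 161 days (23 weeks) after the fourth ends.
- Eight ADA samples fall up to Week 28: Day 1 and Weeks 2, 3, 4, 5, 12, 20 and 28. Seven of them follow the first dose.
- For the Week 1 AUC, two samples (Day 1, Week 2) lie within or at the end of the interval and six come later.
- For the Week 4 AUC, five lie at or before its end and three (Weeks 12, 20, 28) come later.

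**Path 1: ADA lowers AUC.** All rates and effects here are assumed. If ADA-positive patients have AUC multiplied by r, and the products are otherwise equal, the ratio without ADA in the model is r^(p_T − p_R), where p_T and p_R are the ADA rates on SAIT101 and MabThera. The ratio with ADA in the model is 1.00.
- 15% v 5%, r = 0.8: 0.8^0.10 = 0.978, against 1.00 adjusted.
- If half the positives in each arm arise too late to affect the AUC, the early rates are 7.5% v 2.5%. The ratio is then 0.8^0.05 = 0.989, again against 1.00 adjusted.
- Range over other assumptions (simulated ratio without ADA in the model; 1.00 with it throughout):

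| ADA rates | r = 0.8 | r = 0.6 | r = 0.4 |
|---|---|---|---|
| 10% v 5% | 0.988 | 0.975 | 0.955 |
| 20% v 5% | 0.967 | 0.926 | 0.872 |
| 30% v 10% | 0.956 | 0.903 | 0.832 |

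**Path 2: low exposure leads to later ADA, true ratio 1.00.** Simulation of 2,000,000 patients per scenario. The log-odds of ADA fall by 0.5, 1.0 or 1.5 (assumed) per SD of log AUC. The ratio after adjustment is:

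| ADA rates | 0.5 | 1.0 | 1.5 |
|---|---|---|---|
| 10% v 5% | 1.009 | 1.016 | 1.024 |
| 20% v 5% | 1.027 | 1.050 | 1.067 |
| 30% v 10% | 1.036 | 1.066 | 1.086 |

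With equal ADA rates (5% v 5%) there was no shift on either path.

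**Scale.** SE of the log ratio = 0.367 × sqrt(2/60) = 0.067. The 90% CI half-width is about 0.11, giving 0.89 to 1.12 at a ratio of 1.00. The 15% v 5% illustration shifts the log ratio by 0.10 × |ln 0.8| = 0.022, about one-fifth of that half-width.

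**The case against.** The strongest reply is that nothing is decided on this model. Similarity rests on the treatment-only analysis, the adjusted repeat has no decision rule, and any gap between the two would be visible because both are planned. This stands. A reader might infer that the adjustment could hide a real exposure difference in the PK conclusion; the documents do not support that.

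A reader might also infer that this is the only planned scrutiny of the PK result. It is not. SAP 13.2 also summarises PK parameters by region, age category, sex and overall ADA status, and SAP 15 adds ADA status to the primary model. Those summaries are descriptive, and SAP 15 reports the ADA-positive/negative ratio, so this remains the only analysis labelled a sensitivity analysis of the treatment ratio.

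A third tempting reading is that overall ADA status is purely a treatment outcome that mostly arises late. Day 1 pre-dose positives count too, and the documents give no onset times. Late onset would also weaken Path 1, since antibodies that first appear after an interval closes cannot have lowered its AUC. For the same reason, removal of a real effect is more plausible for the Week 4 AUC than for the Week 1 AUC.

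Finally, it is a legitimate explanatory question whether a product difference persists after allowing for antibodies, and the protocol's covariate list is open. That justifies SAP 15. It does not justify presenting the result as a robustness check of the randomised comparison.

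**Conclusion.** The point holds as a minor one. A covariate that is largely post-randomisation, and is itself a compared outcome, enters a model meant to repeat the treatment comparison. If ADA rates differ by arm, that model stops estimating the randomised ratio. The primary PK conclusion, alpha, sample size and power are unaffected.

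The size cannot be read from the documents, which give neither ADA rates nor the effect of ADA on exposure. At 15% v 5% ADA and a 20% lower AUC in positive patients, the effect removed is about 2% at most, well inside the 80–125% limits. The larger shifts in the tables need wider rate differences or stronger effects that no passage supports; they show the range and are not predictions.

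**What to change.** In the covariate list of the SAP 13.2 sensitivity analysis, replace overall ADA status with baseline (Day 1 pre-dose) ADA status, or delete it. Keep age, sex and baseline body weight. All covariates are then fixed before dosing, and baseline ADA status is already planned in SAP 9. Leave overall ADA status to the SAP 15 exploratory analysis and to the PK summaries by treatment and ADA status, so no information is lost.

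This is a free improvement: a few words changed in the SAP before unblinding, with no new data and no effect on alpha, sample size or power.
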